	
standard finger stick microscopic.
 
 
• In the SSAT arm at enrollment, only children who are Pv seropositive and/or LMF Pv/Po positive receive supervised high-dose primaquine (1mg/kg for 7 days) regardless of their symptoms. All blood slides will be processed and read directly after blood collection. Then treatment will follow if positive. Sero-positive children, on the other hand, will commence treatment after the result is available (approximately 1 week). Symptomatic or asymptomatic LMF positive for Pf/Pm will be treated according to current national guidelines.
 
• In the control arm at enrollment, only children who are symptomatic and LMF Pv/Po positive will receive supervised high-dose primaquine (1mg/kg for 7 days).
 
• In both arms at every other timepoint, symptomatic LMF positive children will receive treatment in accordance with national guidelines (unsupervised).
 
• In both arms at the final timepoint, LMF will be conducted on all children and if positive will be treated according to national guidelines.
 
• As blood schizontocides, DHA-PP for 3 days will be given according to body weight (national guidelines).
 

Inclusion and Exclusion Criteria
	
Inclusion:
 
 
• resident of study area and attending selected elementary school in Grade 1-5
 
• no evidence of health condition that would interfere with study participation
 
• assent of child and documented parental informed consent
 
 
Exclusion:
 
 
• G6PD deficiency as determined by SD Biosensor quantitative determination of <70% G6PD activity (male: <4 U/g Hb, female: <6 U/g Hb).
 
• Haemoglobin < 9 g/dL
 

Analysis plan and sample size calculation
	
The study is designed to show a superiority of SSAT vs. routine care for the prevention of recurrent P. vivax infections. The primary study endpoint will be the proportion of children with recurrent P. vivax by PCR during 9 months of follow-up. Secondary endpoints include time-to-first P. vivax recurrence as well as incidence of symptomatic

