### 6.3. Study design and study overview

The study design is a randomized controlled trial with serological screening and treatment as the intervention. Selected schoolchildren will be allocated into two study arms: (1) serological screening and treatment (SSAT), and (2) routine care as control arm.

At enrolment, in the SSAT arm, individuals found *P. vivax* positive by either serological (Luminex) or Giemsa stained microscopic examination regardless of the symptoms will receive supervised treatment (direct observation) with high dose PQ (daily 1 mg/kg BW) for 7 days ( $P_o=P_v$ ). In the control arm, only symptomatic individuals found *P. vivax* positive by Giemsa stained microscopic examination will receive the same regimen ( $P_o=P_v$ ). In addition, in the treated children of both arms, dihydroartemisinin-piperaquine (DHA-PP) will be given as blood schizontocide according to body weight. All other species (*P. falciparum*, *P. malariae*) found by Giemsa stained microscopic examination will be treated according to national guideline. Serological examination will be performed by Luminex (done at Eijkman, Jakarta) and point-of-care (POC) antibody detection using rapid test on site

Follow up will be performed monthly for 9 months. During this period, 400  $\mu$ L of finger pricked blood samples will be collected from all children in both arms. These samples will be tested for malaria presence by PCR which will be done at EO CRU, Jakarta. However, children with clinical symptoms (body temperature of  $\geq 37.5^\circ\text{C}$  and/or history of fever within 3 days), will be examined by Giemsa stained microscopy on site, and treated if positive (any species) according to national guideline (unsupervised).

At the last follow up, a mass blood survey will be conducted to both arms for *Pv* serological test, LMF, and PCR. Those found positive by LMF for any species will be treated regardless of their symptoms.

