### **6.10. Gametocyte study**

At enrollment, blood samples will also be taken from shallow vasculature of the skin from the ankle of all participants from both arms for microscopic examination (light microscopic-skin/LMS) (figure 2). Malaria status by LMS will be assessed post-hoc and will not indicate any treatment.

To determine longevity of these skin gametocytes, LMS samples will be taken at monthly follow up. Moreover, to explore any diurnal variation of this stage, we should obtain blood samples at night and during the day. Therefore, during follow up activity, house visit will be made to the malaria infected children with symptoms for collecting two times blood samples, i.e. 7-10 AM and 7-10 PM. In addition, household members will be asked to contribute their blood samples (LMF, LMS, and PCR). For the household members, LMF will be read on site to indicate treatment.

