*Plasmodium* gametocytes prevalence in LMF and LMS will be calculated as the number positive for gametocytes by each diagnostic method divided by the number of subject examined. Diagnostic performance will be derived using  $2 \times 2$  contingency to determine sensitivity, specificity, positive predictive value (PPV), negative predictive value (NPV). Results of qPCR detection will be used as the gold standard for diagnostic method evaluation. All statistics will be reported as absolute values with their 95% confidence interval (95% CI). To assess the significance of different results of LMF and LMS methods, we will apply McNemar's chi-square test on  $2 \times 2$  contingency tables derived from the results of each detection method.

We will evaluate durability analysis by measuring population half-life of the existence of *Plasmodium* gametocyte detected by LMS samples. Gametocyte prevalence-based approach will use data on the appearance and disappearance of any circulating gametocytes according to the prevalence at month 0 and the prevalence at the time when they are fully cleared from skin vasculature.

Sensitivity, specificity, positive predictive value, and negative predictive value of hemozoin detection will be reported using microscopic Giemsa examination as golden standard.

Hemoglobin measurement using Sahli method and Standard G6PD will be compared to HemoCue by t test.

Hemoglobinopathy rate will be reported as descriptive value.

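### The skin-gametocyte half-life in section 8.3 takes no account of baseline treatment, which differs by arm, so over all participants it mixes drug clearance with untreated persistence and, new infections aside, is too short

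*Protocol*

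**What the plan says.** Section 6.10 gives the aim and the sampling: "To determine longevity of these skin gametocytes, LMS samples will be taken at monthly follow up". At enrolment, "blood samples will also be taken from shallow vasculature of the skin from the ankle of all participants from both arms". The skin result has no bearing on care: "Malaria status by LMS will be assessed post-hoc and will not indicate any treatment".

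The analysis is in section 8.3: "We will evaluate durability analysis by measuring population half-life of the existence of" gametocytes found by LMS, using their appearance and disappearance "according to the prevalence at month 0 and the prevalence at the time when they are fully cleared from skin vasculature". Gametocyte prevalence is defined in the same section as positives over everyone examined. Neither sentence names an arm or treatment status. Secondary endpoint IX in section 5.2, mean gametocyte duration by LMS and LMF, is equally unconditioned.

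Treatment at enrolment differs by arm. Under section 6.3, SSAT children positive for *P. vivax* by Luminex or by slide, "regardless of the symptoms will receive supervised treatment (direct observation) with high dose PQ (daily 1 mg/kg BW) for 7 days"; the Synopsis agrees. In the control arm only symptomatic slide-positive children receive that regimen, and *P. ovale* is handled as *P. vivax*. In addition, "in the treated children of both arms, dihydroartemisinin-piperaquine (DHA-PP) will be given as blood schizontocide according to body weight". Section 6.7 puts the first follow-up one month after the last primaquine dose, so all baseline treatment falls between the month-0 and the first follow-up LMS samples.

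**The concern.** Section 4 sets out the hypothesis: gametocytes may be sequestered for a long time in the upper dermis and sustain silent, durable infections there. Testing it requires knowing how long gametocytes persist when nobody has removed them with drugs.

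A prevalence curve over all participants does not show that. Part of the fall between month 0 and the first follow-up is caused by the trial's own treatment, mostly in one arm. A short half-life could then mean that skin carriage is brief, or only that many carriers were treated, and the single figure cannot separate the two. The error runs against the hypothesis under study. Randomisation supplies a group of largely untreated *P. vivax*/*P. ovale* carriers, but the analysis text does not use them separately.

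**Working it through.** The protocol gives no half-life, carrier prevalence or precision for this analysis, so there is no figure to reproduce. What can be checked is how far an all-participant half-life would move under stated assumptions.

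**From the protocol.** Allocation is 1:1, 400 per arm (Synopsis). LMS is monthly, with nine months of follow-up (sections 6.3 and 6.10). Baseline treatment precedes the first follow-up LMS (section 6.7).

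**Assumed, because the protocol does not say.**
- f, the share of month-0 LMS carriers in the SSAT arm who are treated and cleared before the first follow-up: 0.3 to 1.0. School seroprevalence of 30-70% (section 6.2) is only a rough guide to it.
- g, the same share in the control arm: 0, with 0.1 as a variation.
- h, the half-life in untreated carriers: 3, 6 or 12 months, with exponential loss.
- Complete clearance in the share f, no new infections, carriers split equally between arms, first follow-up taken as month 1.

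**Formulas.** With k = 1 − (f + g)/2, the fraction of carriers left untreated:

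- relative prevalence at month t: P(t)/P(0) = k × 0.5^(t/h)
- apparent half-life from months 0 and t: H = t × ln 2 / ln(P(0)/P(t))

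**Worked for h = 6, g = 0.**
- f = 1, k = 0.50. Month 1: 0.50 × 0.891 = 0.445, so H = 0.693/0.809 = 0.86. Month 9: 0.50 × 0.354 = 0.177, so H = 9/2.5 = 3.60.
- f = 0.3, k = 0.85. Month 1: 0.85 × 0.891 = 0.757, so H = 0.693/0.278 = 2.49. Month 9: 0.85 × 0.354 = 0.301, so H = 9 × 0.693/1.202 = 5.19.

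**Apparent half-life in months, g = 0.**

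| True h | f = 1.0, months 0-1 | f = 0.7, months 0-1 | f = 0.3, months 0-1 | f = 1.0, months 0-9 | f = 0.7, months 0-9 | f = 0.3, months 0-9 |
|---|---|---|---|---|---|---|
| 3 | 0.75 | 1.05 | 1.76 | 2.25 | 2.49 | 2.78 |
| 6 | 0.86 | 1.27 | 2.49 | 3.60 | 4.24 | 5.19 |
| 12 | 0.92 | 1.42 | 3.15 | 5.14 | 6.56 | 9.14 |

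With g = 0.1 the values are somewhat lower and the pattern is the same; for h = 6, months 0-1 give 0.76-2.05 and months 0-9 give 3.39-4.94.

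Two intervals are shown because section 8.3 does not settle the estimator. Taken literally, prevalence at full clearance is zero, and the logarithm of P(0)/0 is infinite, so a two-point half-life from those inputs is undefined.

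**After the fix.** Restricting to untreated carriers sets k = 1, and the formula returns H = h: 3, 6 and 12 months come back as 3, 6 and 12.

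**The case against.** Section 8.3 does not say that the arms are pooled, and sampling in both arms does not define the analysis set. Stratification and censoring are often left to a SAP, which is not at hand. This stands as far as it goes: pooling is the natural reading, not an express statement. But the protocol has already chosen a population-level half-life from prevalence among all those examined, and whose persistence is measured belongs to the definition of the quantity.

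A reader might infer that nearly every SSAT carrier is treated. The documents do not support this. Treatment follows serology or finger-stick microscopy and never LMS, so a seronegative, LMF-negative skin carrier stays untreated in the SSAT arm too. The serology is specific to *P. vivax*, and section 6.3 treats *P. falciparum* and *P. malariae* found by microscopy under national guidelines without limiting this to one arm. The sharp contrast between arms therefore concerns *P. vivax*/*P. ovale*.

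New infections also matter. Relapse or reinfection raises later prevalence and lengthens an all-participant half-life. That is a second contamination in the other direction, not a remedy.

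Finally, the objective and endpoint do not use the word untreated. That is fair, but the hypothesis in section 4 and the longevity aim in section 6.10 make it the sensible reading. The endpoint is secondary and affects neither the primary comparison nor safety.

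**Conclusion.** The point holds. As written, the durability analysis disregards a treatment difference that the trial itself creates between the month-0 and first follow-up samples. An all-participant half-life mixes drug clearance with untreated persistence and, new infections aside, is biased downward. The amount depends on the treated share among LMS carriers and on the estimator, and the documents give neither. With 30-100% of SSAT carriers treated and cleared, no treated controls and no new infections, a true 6 months reads as about 0.9-2.5 months from months 0-1, or 3.6-5.2 months from months 0-9.

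A reader might go further and infer that the estimate falls to about one month whatever the true duration. That needs nearly all SSAT carriers cleared and a half-life read from the first interval alone, which the protocol does not specify. Over months 0-9, even with every SSAT carrier cleared, true values of 3, 6 and 12 months give 2.25, 3.60 and 5.14: too low, but clearly distinct.

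This is a worthwhile correction to a stated method for a secondary endpoint.

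**What to change.** In section 8.3, take the main longevity estimate from control-arm children who are LMS gametocyte-positive at month 0 and not treated at baseline. Follow each child to loss of LMS gametocytes, so that new carriers do not enter the estimate, and censor at the first antimalarial treatment for any species. Report treated children from either arm separately, as post-treatment clearance. Do not use an all-participant half-life as the longevity estimate. Apply the same definition to the LMS part of endpoint IX.

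No procedure changes, since arm, treatment records and monthly LMS are already collected. The cost is fewer carriers and a wider interval. Two limits should be acknowledged in the text: relapse or reinfection can make gametocytes reappear in a child and look like persistence, and censoring at symptomatic treatment may be informative.

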The current standard for the diagnosis of malaria in ill patients or healthy residents of endemic areas perform poorly at parasite counts below 50 per microliter blood (11,12). Nucleic acid-based diagnostic techniques offer relatively much greater sensitivity (i.e., from approx. 1/uL to 1/mL), but these assays cannot be done at point-of-care (a sophisticated laboratory and equipment are required), takes days or weeks to complete, requires highly specialized training, and imposes prohibitive direct costs (13). Malaria research leaders and communities identified and acknowledged the need for a point-of-care diagnostic tool with PCR-like sensitivity as a critical need (14,15). The simple, practical, and inexpensive approach to a bedside diagnosis within an hour would effectively empower mass screening and treatment as a means of interrupting malaria transmission in endemic communities, whereas today that practice is futile due to the weakness of diagnostic technology

and the epidemiological dominance of clinically silent sub-patent parasitemias (5). In search of point-of-care diagnostic test, potential of hemozoin as detection tool will also be explored. Previous studies employing magnetic field to capture hemozoin have demonstrated strong preference for gametocytes and increased sensitivity for detection of *P. vivax* asexual stages (16,17). This project will investigate the performance of a point-of-care diagnostic tool employing magneto-optical detection in ankle/feet area which can provide further evidence for the skin reservoir hypothesis.

Moreover, previous studies have demonstrated a higher rate of hemoglobinopathy in malarious areas due to evolutionary pressure (18). Apart from its controversial benefit against malaria, this trait brings substantial health problem to individuals carrying it. This project will investigate the rate of hemoglobinopathy in schoolchildren.

Lastly, radical cure of *P. vivax* is crucial part to stop malaria transmission, therefore compliance and safety monitoring of currently available hypnozoitocidal PQ is essential (19). This project will contribute evidence towards the development of guidelines for high dose PQ in Primary Health Center to establish its use in national scale. The utilisation of cheap and widely used Sahli's Hb measurement for such purpose will be evaluated as well.

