### **5.2. Secondary objectives:**

1. To evaluate the performance of a point-of-care (POC) anti-*P. vivax* antibody detection test relative to Luminex (MagPix).
2. To evaluate safety of high dose PQ administration in schoolchildren.
3. To evaluate the accuracy of Sahli's method and Standard G6PD (SD Biosensor Inc., Deogyong-daero, Korea) relative to HemoCue for haemoglobin measurement.

4. To estimate the sensitivity and specificity of a microscopic diagnosis of blood by sample from skin (ankle) relative to standard finger stick microscopic and PCR.
5. To measure duration of gametocyte in the blood samples of the skin of the ankle and finger prick.
6. To estimate the sensitivity and specificity of magneto-optical hemozoin detection by Gazelle® (Hemex Health, USA) relative to standard finger stick microscopic and PCR. To analyse hemoglobinopathies in schoolchildren using HemeChip by Gazelle (Hemex Health, USA)

*Primary endpoint:* the proportional reduction of *P. vivax* incidence by PCR in children serologically screened relative to those receiving routine care during 9 months of active follow-up.

*Secondary endpoints:*

- (I) Difference in the time-to recur of *P. vivax* by PCR in SSAT and control arms.
- (II) Difference in the number of recurrent *P. vivax* by PCR in SSAT vs. control arms.
- (III) Difference in the incidence of recurrent symptomatic *P. vivax* by LMF in SSAT vs control arms.
- (IV) Seroconversion rate before and after intervention in SSAT and control arms.
- (V) Sensitivity and specificity of POC antibody detection test vs. gold standard Luminex assay.
- (VI) Adverse event (AE) and Severe Adverse Event (SAE) of high dose PQ in schoolchildren.
- (VII) Hb level in Sahli's method, Standard G6PD (SD Biosensor Inc., Deogyong-daero, Korea), and Gazelle® (Hemex Health, USA), in comparison with HemoCue (HemoCue AB, Angelholm, Sweden).
- (VIII) Sensitivity and specificity of microscopic examination to detect parasitemia from the shallow skin vasculature of the ankle (light microscopy-skin/LMS) compared to standard microscopic (light microscopy-finger/LMF) and PCR.

- (IX) Mean duration time of gametocyte in LMS and LMF
- (X) Sensitivity and specificity of magneto-optical hemozoin detection (MOD) compared to standard malaria detection and PCR.
- (XI) Sensitivity and specificity of Standard G6PD (SD Biosensor, Inc., Deogyong-daero, Korea Korea) compared to CareStart G6PD RDT (Access Bio. Inc., New Jersey, USA).

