**Exclusion:**

- G6PD deficiency as determined by SD Biosensor quantitative determination of <70% G6PD activity (male: <4 U/g Hb, female: <6 U/g Hb).
- Haemoglobin < 9 g/dL as determined by HemoCue.

These subjects will be referred to PHC for treatment.

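### Section 8.3 judges the accuracy of Hb methods by a t test alone, and names only microscopy as the reference for hemozoin detection where the objective and endpoint also name PCR

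*Protocol*

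**What the plan says.** **Haemoglobin.** Objective 3 in Protocol Section 5.2 (III in the synopsis) is "To evaluate the accuracy of Sahli's method and Standard G6PD", with HemoCue as the comparator. Endpoint VII lists the same two methods and adds a third: "and Gazelle® (Hemex Health, USA), in comparison with HemoCue (HemoCue AB, Angelholm, Sweden". The only analysis, in Section 8.3, is "Hemoglobin measurement using Sahli method and Standard G6PD will be compared to HemoCue by t test". It does not say whether the test is paired, names no measure of agreement, and does not mention Gazelle. The background (Section 4) gives the purpose in a paragraph on the safety of primaquine in primary care: "The utilisation of cheap and widely used Sahli's Hb measurement for such purpose will be evaluated as well". The trial itself applies a threshold to individual readings at entry: "Haemoglobin < 9 g/dL as determined by HemoCue".

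**Hemozoin detection (MOD).** Objective 6 asks for sensitivity and specificity relative to finger-stick microscopy and PCR. Endpoint X likewise concerns "magneto-optical hemozoin detection (MOD) compared to standard malaria detection and PCR". Section 8.3 states that the accuracy measures for "hemozoin detection will be reported using microscopic Giemsa examination as golden standard". Earlier in Section 8.3, in the paragraph on gametocytes by finger and skin microscopy (LMF and LMS), another sentence makes qPCR the gold standard for evaluating diagnostic methods. Section 4 says that current standard diagnostics "perform poorly at parasite counts below 50 per microliter blood".

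**The concern.** Accuracy of a measuring method is a question about how far one child's reading may lie from the reference reading. A test of equal means does not address it: large errors in both directions cancel, and a small constant shift becomes significant once the sample is large. A non-significant result could be reported as showing that Sahli is accurate, and a significant one as showing that it is not, with neither statement supported. Since Sahli is being looked at for use in individual patients, this could mislead.

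For MOD, the plan assigns an analysis to one of the two comparisons that the endpoint names. If the hemozoin sentence is followed literally, a child who is MOD-positive, PCR-positive and slide-negative is scored as a false positive. By the protocol's own account of microscopy, low-density infections are where this will happen.

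**Working it through.** The protocol gives no sample size, power or expected accuracy for these objectives, so there is no stated figure to reproduce. What follows illustrates the consequence of the stated analyses.

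**Inputs from the protocol**
- 800 schoolchildren (synopsis), with HemoCue, Sahli and Standard G6PD run on the same enrolment tube (Sections 6.6 and 7.2), so the readings are pairs.
- *P. vivax* PCR prevalence of about 20%, from a 2013 study (Section 8.2).
- Hb cut-off of 9 g/dL (Section 6.4).

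**Assumptions**
- Two-sided 5% level for the t test.
- SD of within-child differences 0.5 to 2.0 g/dL; mean bias 0 or 0.1 g/dL.
- MOD specificity of 98% against PCR; microscopy finds a fraction s = 0.3 to 0.5 of PCR positives; MOD finds a fraction m = 0.3 to 0.7 of the PCR positives that microscopy misses, and 90% of those that it finds.

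**Step 1: Hb, zero mean bias.** Limits of agreement are bias ± 1.96 × SD.

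| SD of differences (g/dL) | 95% limits (g/dL) | P(t test non-significant) |
|---|---|---|
| 0.5 | ±0.98 | 0.95 |
| 1.0 | ±1.96 | 0.95 |
| 1.5 | ±2.94 | 0.95 |
| 2.0 | ±3.92 | 0.95 |

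The test gives the same answer across a fourfold range of individual error.

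**Step 2: Hb, bias 0.1 g/dL, 800 pairs.** Noncentrality = bias × √n / SD.
- SD 0.5: 0.1 × 28.28 / 0.5 = 5.66; power about 1.00; limits −0.88 to 1.08 g/dL.
- SD 1.0: 0.1 × 28.28 / 1.0 = 2.83; power 0.81; limits −1.86 to 2.06 g/dL.

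The method with tighter agreement is rejected more often. If the test were run unpaired, power for the same bias would be 0.52 at a between-child SD of 1.0 g/dL and 0.27 at 1.5 g/dL, so the result would also depend on a choice that the protocol does not state.

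**Step 3: precision of the alternative.** The 95% CI half-width of each limit of agreement is 1.96 × √(1/n + 1.96²/(2(n−1))) × SD. With n = 800 this is 0.118 × SD, so the sample is ample for estimating limits.

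**Step 4: MOD specificity against microscopy.** With PCR prevalence p,

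apparent specificity = 1 − [p(1−s)m + (1−p) × 0.02] / (1 − ps).

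- p = 0.20, s = 0.3, m = 0.7: 1 − (0.098 + 0.016)/0.94 = 0.879.
- p = 0.20, s = 0.5, m = 0.3: 1 − (0.030 + 0.016)/0.90 = 0.949.
- p = 0.05, s = 0.3, m = 0.7: 1 − (0.0245 + 0.019)/0.985 = 0.956.
- p = 0.05, s = 0.5, m = 0.3: 1 − (0.0075 + 0.019)/0.975 = 0.973.

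Against PCR, specificity is 98% in all four cases.

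**Step 5: MOD sensitivity.** Against microscopy it is 90% by assumption. Against PCR it is 0.9s + (1−s)m: from 0.27 + 0.21 = 0.48 (s = m = 0.3) to 0.45 + 0.35 = 0.80 (s = 0.5, m = 0.7). The two references answer different questions in both directions, which is why the endpoint's naming of both matters.

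**The case against.** - *PCR is not excluded.* The qPCR sentence in Section 8.3 is worded generally, so a reader could take it to cover MOD. This stands in part. The sentence is placed in the LMF/LMS paragraph, and the later hemozoin sentence names a different standard. If the first is general, Section 8.3 contradicts itself; if it is local, the PCR comparison has no stated analysis. One might infer that MOD will never be compared with PCR, but the text does not establish that.
- *Microscopy is a legitimate reference.* This stands. The objective and the endpoint ask for it, so the planned MOD analysis answers one of two questions. It would go too far to say that it cannot answer the objective, or that qPCR must rank above microscopy: neither passage sets an order.
- *The figures are illustrative.* This stands. Only the 800 and the 20% come from the protocol, and the 20% is for *P. vivax* alone, whereas Section 7.7 describes a malaria positive/negative result without species. At 5% prevalence the loss of specificity is only about 1 to 2 percentage points. The direction does not depend on the chosen values.
- *Poor Hb agreement might seem to endanger the trial's own rule on falls in Hb.* A reader might set the limits of agreement against a 20% fall from 9 g/dL. The documents do not support that. A fall is measured serially within a child, where a constant difference between methods cancels, and Section 6.8 and Appendix H assign monitoring on treatment to HemoCue, with Sahli at day 0 only.
- *These are substudies.* This stands. Enrolment treatment rests on microscopy and Luminex, and Hb eligibility on HemoCue.

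**Conclusion.** Wrong as written, for two secondary objectives of unequal strength.

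The Hb point holds fully. Section 8.3 fixes a t test as the only analysis of an accuracy objective, and no other section supplies a measure of agreement. That the test is blind to individual error follows from what it tests; the sizes (±0.98 to ±3.92 g/dL with the same result; rejection about 1.00 against 0.81) rest on assumed SDs, an assumed bias and a paired test.

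The MOD point is an inconsistency to reconcile: two references in the objective and endpoint, one in the hemozoin sentence, and a qPCR sentence of unclear reach in the same section. Taken literally, it leaves the PCR comparison unreported and lowers apparent specificity from an assumed 98% to about 88–95% at 20% prevalence, or about 96–97% at 5%.

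The primary efficacy conclusion is not affected by either.

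**What to change.** In Section 8.3:

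1. Replace the t test with paired mean bias and 95% limits of agreement, each with a 95% CI, for Sahli and Standard G6PD against HemoCue. Add agreement in classification at the 9 g/dL exclusion cut-off. That table must include children measured at enrolment and then excluded for low Hb; otherwise it has no HemoCue reading below the cut-off.
2. Treat Gazelle Hb the same way, since endpoint VII names it. Section 7.7 describes haemoglobin typing by that device but no Hb concentration; if it gives none, correct endpoint VII instead.
3. Reconcile the hemozoin and qPCR sentences, and state that MOD sensitivity and specificity are reported with 95% CIs against both enrolment qPCR and microscopy.

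The cost is a few sentences. HemoCue, Sahli, Standard G6PD, MOD, microscopy and qPCR are all scheduled for every child at enrolment (Sections 6.6, 6.11 and 7.8; Appendix H), so these comparisons need no extra samples or visits.
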